The sample dimension was calculated using $\alpha = 0.05$ and the power of 80%. For the standard deviation (SD), the value of 0.8 mm obtained in a previous paper (Jepsen et al. 2013). Thus, study was powered to detect a minimum clinically significant difference in root coverage of 0.8 mm between the test and control treatments for root coverage after 6 months. On the basis of these data, the minimum needed number of

patients to be enrolled in this study resulted 28 for the test group (CAF) and 28 for the control group (CAF+ES).

Randomization, allocation concealment, and blinding

The randomization process was performed by an external person who did not participate in the study. Patients were assigned to one of the two treatment groups with the use of computer-generated randomization sequence. Allocation concealment was obtained using sealed coded opaque envelope containing the treatment to the specific subject. The sealed envelope containing the treatment assignment was opened immediately after the surgical procedure by the investigator responsible for the electrical stimulation protocol. The surgeon, patients and investigators who performed clinical measurements were blinded to procedures.

Surgical procedure

All surgical procedures were performed by a single operator ([name]). With a blade 15c (Surgi Blade® - Miami, FL - USA) two horizontal incisions were made at the bases of the mesial and distal papillae of the tooth, towards the adjacent teeth, taking care not to touch the adjacent teeth. From the end of the incisions, two divergent relaxing incisions were performed vertically in the apical direction that surpassed the mucogingival line so that the flap had mobility for coronary traction. A sulcular incision was performed in order to unite the releasing incisions and a split-full-split thickness flap was raised beyond the mucogingival junction (MGJ) (de Sanctis & Zucchelli 2007). After the root planing procedures were performed, the epithelial layer was removed from the incised papillae exposing the connective tissue. Before the flap was positioned coronally, the region was washed copiously with physiological solution to remove the clot allowing intimate contact of the flap with the recipient bed. Sling sutures (5.0 Vicryl™; Ethicon Inc, São José dos Campos, Brazil) were placed to stabilize the flap 2 mm coronal to CEJ, followed by interrupted sutures to close the releasing incisions.

Electric Stimulation Protocol

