The patients allocated in the CAF+ES group received the protocol for electrical stimulation. A unit consisting of a signal generator (Keysight Technologies., Inc., Santa Rosa-CA, USA), a power supply and circuit board, was assembled. Conductive electrodes for electrical current application were positioned on each side of the flap, at a

mean distance of 3 mm from the relaxing incisions and an alternating current with intensity of 100 μ A at 9 kHz, was distributed in order to traverse the operated region. Patients received the stimulus applications for 120 seconds, once a day for 5 consecutive days. The electrical current was optimized through an oscilloscope (Keysight Technologies., Inc., Santa Rosa-CA, USA). All applications were performed by a single researcher involved in the study ([name]). Patients randomized to the CAF group received the simulation of the electrical stimulation process.

Clinical Assessments

Clinical parameters were evaluated at baseline, 3 and 6 months postoperatively as follows: 1) full-mouth visible plaque index (FMPI) (Ainamo & Bay 1975), and presence or absence of visible plaque accumulation at the site included in the study (plaque index [PI]); 2) full-mouth sulcus bleeding index (FMBI) (Muhlemann & Son 1971), and presence or absence of bleeding on probing (BOP) at the site included in the study; 3) PD: measured in millimeters with a periodontal probe (XP23/UNC-15, Hu-Friedy, Chicago, IL); 4) relative GR (RGR): distance from the gingival margin to the incisal border of the tooth; 5) RCAL: measured as PD+RGR; 6) GR: measured at the mid-buccal aspect of the tooth (both RGR and GR quantified using a caliper with a precision of 0.01mm and a pair of dividers); 7) keratinized tissue width (KTW); and 8) keratinized tissue thickness (KTT): measured at the midpoint location between the gingival margin and mucogingival junction as previously described (Fernandes-Dias et al., 2015). A masked and calibrated investigator ([name]) carried out all clinical evaluations. The examiner calibration was performed for PD and RGR using Kappa statistic and intra-class correlation ($k = 0.88$ and $ICC = 0.81$, respectively).

Esthetic evaluation

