Levels of Cito / chemokines were determined by a multiplex immunoassay. Aliquots of each GCF sample were tested using a commercial human kit (Millipore Corporation, Billerica, MA, USA), in order to evaluate levels of the following inflammatory markers: interleukin (IL)-1 β , IL-6, IL-10, tumoral necrosis factor α (TNF α), macrophage inflammatory protein-1 α (MIP-1 α), and chemotactic protein for monocytes-1 α (MCP-1 α). In addition, matrix metalloproteinases (MMP)-2, MMP-9, tissue inhibitor of metalloproteinases (TIMP)-1, TIMP-2 and VEGF were also evaluated. Sample concentrations (antigens in gingival crevicular fluid samples) were estimated from the standard curve using standard kit proteins following manufacturer's instructions and expressed as pg / mL.

STATISTICAL ANALYSIS PLAN

Descriptive statistics were performed using mean \pm standard deviation (SD), and normality was tested using Shapiro-Wilk tests. The PD, RGR, CAL, KTT, KTW, and DH values and also inflammatory markers / growth factors were examined by two-way repeated measures ANOVA to evaluate the differences within and between groups, followed by a Tukey test for multiple comparisons when the Shapiro-Wilk p value was ≥ 0.05 . Data presenting Shapiro-Wilk p values < 0.05 were analyzed using Mann-Whitney tests (for intergroup comparisons) and a Friedman test (for intragroup comparisons). Postoperative discomfort, patient's esthetics measured through VAS and intergroup RES comparisons were analyzed by T-tests. The frequency of complete root coverage (CRC) was compared using χ^2 tests. For all tests a significance level of 0.05 was adopted.

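### Complete root coverage is compared by an unadjusted chi-square although baseline recession depth is recorded; adjusting for it is a cheap efficiency gain, not the correction of an error

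*Combined protocol and SAP*

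**What the plan says.** - **CRC test.** Statistical Analysis Plan: "The frequency of complete root coverage (CRC) was compared using" chi-square tests. It names no covariate or stratification, and it gives CRC neither a definition nor a time point. It adds: "For all tests a significance level of 0.05 was adopted".
- **Baseline depth.** Clinical Assessments: "Clinical parameters were evaluated at baseline, 3 and 6 months postoperatively as follows". The list that follows includes "GR: measured at the mid-buccal aspect of the tooth", read with a caliper to 0.01 mm.
- **Range of depth.** Study Population sets a floor of 3 mm for recession depth and no ceiling.
- **Allocation.** The randomisation section describes a computer-generated sequence and mentions no stratification or balancing on depth.
- **What the trial was sized for.** Sample size refers to a "minimum clinically significant difference in root coverage of 0.8 mm between the test and control treatments" at 6 months. CRC plays no part in that calculation.

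**The concern.** CRC is taken here to mean a residual GR of zero. On that reading, the coverage a patient needs equals the depth at entry: a 5 mm recession needs 2 mm more coverage than a 3 mm one to count as a success. Depth is therefore a natural predictor of CRC, and it is already collected. An unadjusted test leaves the variation due to depth in the comparison. If depth is prognostic, this costs power, and the one observed CRC difference is harder to interpret when the arms happen to differ in depth. What is at stake is precision on a binary outcome in a trial of 60 patients, recoverable at the analysis stage without recruiting anyone.

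**Working it through.** **1. The plan's own figure.** The only power calculation concerns root coverage in mm. Its inputs are alpha 0.05 (two-sided assumed), "and the power of 80"%, SD ("the value of 0.8 mm obtained in a previous paper") and a difference of 0.8 mm.

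n per group = 2(z₀.₉₇₅ + z₀.₈₀)²(SD/difference)² = 2(1.960 + 0.842)²(0.8/0.8)² = 2 × 7.85 = 15.7, so 16 (17 with the t distribution).

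The plan states "28 for the test group (CAF) and 28 for the control group (CAF+ES"). These inputs do not reproduce 28; at 28 per group the power for 0.8 mm would be about 96%. That is a separate matter. Here it shows only that no figure in the plan covers CRC.

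**2. Assumptions needed for CRC.** The documents give none of these:
- 30 per arm (60 patients split equally);
- CRC rates of 40% and 70%;
- baseline depth SD of 0.8 mm. The plan's 0.8 mm SD belongs to its root-coverage calculation, not to depth at entry;
- a depth–CRC odds ratio per mm, meaning the factor by which the odds of CRC fall for each extra mm, varied from 1 (no association) to 5.

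**3. Chi-square power.** Power = Φ{[|p₁ − p₂|√n − 1.96√(2p̄(1 − p̄))] / √(p₁(1 − p₁) + p₂(1 − p₂))}. With p̄ = 0.55:
- 0.30 × √30 = 1.643;
- 1.96 × √0.495 = 1.379;
- √(0.24 + 0.21) = 0.671;
- Φ(0.264/0.671) = Φ(0.394) = 0.65.

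For 50% versus 75% the same formula gives 52%, and for 50% versus 80% it gives 69%.

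**4. Power after adjustment.** Simulation with 4,000 trials per setting: depth is 3 mm plus a gamma variable with SD 0.8 mm, and marginal CRC rates are held at 40% and 70%. It compares the likelihood-ratio test for arm in a logistic model containing depth with the uncorrected chi-square. Repeated runs gave:

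| Assumed odds ratio per mm | Chi-square power | Adjusted power | Gain (points) |
|---|---|---|---|
| 1 | 64–67% | about 67% | about 0 |
| 2 | 64–67% | 69% | 3–4 |
| 3 | 64–67% | 71–74% | 6–7 |
| 5 | 64–67% | 76–77% | about 10 |

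Simulation error is about 0.7 points per estimate: √(0.67 × 0.33/4000) = 0.007. With a depth SD of 0.5 mm the gains shrink to about 0, 2, 2 and 5 points.

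**5. Cross-check on a different scale.** A second simulation used normally distributed depth and odds ratios per SD of 1.0, 0.61, 0.37, 0.22 and 0.14. It compared adjusted with unadjusted likelihood-ratio tests, so the gain reflects adjustment alone. Over the three pairs of rates in step 3, the gain was about −1 to 0, 2–3, 7–8, 12–14 and 17–20 points. Those odds ratios are exp(−0.5), exp(−1), exp(−1.5) and exp(−2) after the first. At an SD of 0.8 mm they correspond to about 1.9, 3.5, 6.5 and 12 per mm (for example exp(1/0.8) = 3.5). The largest gains therefore need a very steep relation.

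**6. Type I error.** With 50% CRC in both arms, the second simulation's chi-square rejected in 4.4–5.3% of trials and its adjusted test in 5.0–6.1%. A small part of each gain is therefore slightly looser error control.

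**7. Chance imbalance.** The standard error of the between-arm difference in mean depth is 0.8 × √(2/30) = 0.21 mm, a 95% range of about ±0.40 mm.

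**The case against.** The strongest reply is that nothing here is wrong. Under randomisation the chi-square is a valid test, and its error rate already allows for chance imbalance in depth. A reader might infer that the CRC comparison is biased because depth is ignored. The documents do not support that, and the null rejection rates above contradict it.

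A reader might also take CRC to be a key outcome, or the only root-coverage outcome with a named test. No section designates it so. RGR, the distance from gingival margin to incisal border, is in the repeated-measures ANOVA list, and its change tracks root coverage in mm. GR and root coverage in mm are not themselves named there, but that is a different point.

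Finally, a reader might infer a definite loss of power. The size depends on CRC rates, a depth SD and an association that the documents do not report, and zero gain is possible. At 40% versus 70%, adjusted power stays below 80% for every odds ratio up to 5 per mm, so adjustment does not make the trial adequately powered for CRC.

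All of this stands. What remains is that a baseline value already in hand goes unused for an outcome whose target it sets. Using it costs essentially nothing if depth turns out not to matter.

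**Conclusion.** The point holds as a low-cost improvement in efficiency and precision. It is neither an error nor a source of bias. Under the stated assumptions the gain in power runs from nil to about 10 percentage points for depth odds ratios of 1 to 5 per mm. It is smaller if depth varies less, and larger only if the association is steeper. The facts that support it are in the documents: an unadjusted test, a recorded baseline depth with no upper limit, and no described stratification by depth. Its magnitude rests entirely on assumed values and should be presented as a range.

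**What to change.** - Define CRC as GR = 0 and state that it is assessed at 6 months, the time point of the outcome used for sample size.
- Analyse it by logistic regression on treatment arm and baseline GR (continuous, in mm).
- Report the standardised risk difference (predicted CRC averaged over all patients' baseline depths under each arm) with a 95% CI.
- Keep the chi-square as a supportive unadjusted result.

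The cost is a few lines of SAP text and one extra model, with no additional patients, visits or measurements. The one drawback is that the model's odds ratio is conditional on depth and is not comparable with the crude odds ratio, so the standardised risk difference should be the effect reported. The plan is written in the past tense; if CRC results by arm have already been seen, the adjusted analysis should be labelled post hoc.

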To assess the final aesthetic outcome, two analyses were performed, one professional e one patient-centered. The professional evaluation was assessed using the Root Coverage Esthetic Score (RES) (Cairo et al. 2009). For this, two examiners performed the evaluations ([name] and [name]) 6 months after surgeries. The examiners presented previous experience in cosmetic dentistry, were blinded for the treatments and were previously calibrated (intra and inter-examiners $K>0.8$). Esthetic outcomes were also evaluated from the patient's point of view, using a VAS scale pre- and 6 post-operative.

Patient-centered outcomes

At the end of the first postoperative week, the patients completed a questionnaire about the occurrence of discomfort and postoperative pain. The pain was rated by the patient on a VAS scale of 0 to 10 (0 = no sensitivity and 10 = extreme pain). In addition, the patients were asked to report the number of analgesic pills they consumed that week. Dentin hypersensitivity was assessed by 5 s air blast from a triple syringe, applied to the exposed buccal cervical area. A visual analogue scale (VAS) scale (0 = no pain, 10 = extreme pain) was used to record DH related to stimulus. DH was recorded at baseline, 3 and 6 months postoperatively.

Sampling and immunological evaluation

The samples were collected as previously described (Santamaria et al., 2013). Briefly, gingival crevicular fluid (GCF) was collected from the vestibular region of the site that received the CAF. Sampling was performed by introducing filter paper strips (Periopaper; Proflow Inc., Amityville, NY, USA) into sulci until mild resistance was felt, removed after 20 s, and collected fluid volume immediately determined by calibrated instrument (Periotron 8000; Ora Flow Inc., Plain View, NY, USA). The strips were placed in sterile tubes containing 300 ml of phosphate buffered saline (PBS) with 0.05% Tween-2. Strips contaminated with visible blood were discarded. All GCF samples were stored immediately at -80° C. Samples were collected at baseline (before surgery), and 7, 14, 30, 60 and 90 days after surgery.

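### Eleven GCF markers are each tested at 0.05 with no adjustment across markers, and the rule for declaring a between-arm marker difference is not stated

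*Combined protocol and SAP*

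**What the plan says.** The section on sampling and immunological evaluation lists six inflammatory markers (IL-1β, IL-6, IL-10, TNFα, MIP-1α, MCP-1α) and then five more: "In addition, matrix metalloproteinases (MMP)-2, MMP-9, tissue inhibitor of metalloproteinases (TIMP)-1, TIMP-2 and VEGF were also evaluated". That makes 11. On timing it says: "Samples were collected at baseline (before surgery), and 7, 14, 30, 60 and 90 days after surgery".

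The Statistical Analysis Plan has two branches, chosen by a Shapiro-Wilk test. In the first, the markers are "examined by two-way repeated measures ANOVA to evaluate the differences within and between groups". The only multiplicity procedure named sits in this branch, on condition that the normality test gives 0.05 or more: "followed by a Tukey test for multiple comparisons when the Shapiro-Wilk p value was". In the second, data "were analyzed using Mann-Whitney tests (for intergroup comparisons) and a Friedman test (for intragroup comparisons"). The level is common to everything: "For all tests a significance level of 0.05 was adopted".

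The Sample size section concerns one outcome, assessed at 6 months: the "study was powered to detect a minimum clinically significant difference in root coverage of 0.8 mm between the test and control treatments". The SAP labels neither the markers nor the other outcomes as secondary or exploratory.

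**The concern.** A 5% level per test does not give a 5% error rate for a set of 11 markers. If one marker reaches p < 0.05, the plan as written allows it to be reported as a biological effect of electrical stimulation, although such a result somewhere in the set may be likely by chance.

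Three omissions make the size of the problem hard to pin down:

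- In the ANOVA branch, the SAP does not say whether a between-arm finding is a significant group term, a significant group-by-visit term, or a Tukey contrast.
- For Tukey, it does not give the set of means compared or the error term.
- In the Mann-Whitney branch, one test per visit is the likely intention but is not stated.

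What is at stake is the credibility of the marker and mechanism claims, not the clinical outcome on which the trial was sized.

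**Working it through.** The plan gives no error rate for the markers as a set, so there is no figure of its own to reproduce beyond 0.05 per test.

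**Inputs from the documents.** Markers: 6 + 5 = 11. Post-surgery visits: 5, plus baseline, so 6 times. Level: 0.05 per test. Patients: 60, taken as 30 per arm.

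**Assumptions.** No marker is affected. Tests are two-sided (sidedness is not stated). A common correlation r applies between markers and, where visits enter, between visits. The documents give no value of r, so a range is shown.

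**1. One between-arm test per marker (11 tests).**

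- Independent: 1 − 0.95^11 = 0.431.
- Equicorrelated: 1 − ∫ φ(u) [Φ((c − √r·u)/√(1−r)) − Φ((−c − √r·u)/√(1−r))]^11 du, with c = 1.96. This gives 0.375, 0.304, 0.223 and 0.131 at r = 0.3, 0.5, 0.7 and 0.9.
- Simulated t-tests at r = 0.7 with 30 per arm give 0.227. One-sided testing at r = 0.7 would give 0.193.

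**2. All markers to Mann-Whitney, one test per post-surgery visit (11 × 5 = 55 tests).**

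- Independent: 1 − 0.95^55 = 0.940.
- Simulated correlated normal statistics: about 0.88, 0.76, 0.54 and 0.24 at r = 0.3, 0.5, 0.7 and 0.9.

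**3. All markers to ANOVA.** The answer depends on the unstated decision rule.

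- Group and group-by-visit terms both read at 0.05 (22 tests): 1 − 0.95^22 = 0.676 if independent, and a little over 0.4 by simulation at r = 0.7.
- Claims rest only on Tukey over all 2 × 6 = 12 group-by-visit means, counting same-visit between-arm differences after surgery, with a pooled cell variance as error: about 4% to 6% for r from 0 to 0.7.
- Same contrasts with the within-subject error: about 6% at r = 0, rising to about 65% at r = 0.7. That error term leaves out between-patient variation, so it is too small for a comparison between arms, and increasingly so as r grows.

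**4. Price of adjusting.** If only one marker is affected, its Benjamini-Hochberg threshold is about 0.05/11 = 0.0045. For an assumed 0.8 SD effect at one visit with 30 per arm, a single Mann-Whitney test has about 84% power at 0.05 and about 51% at 0.0045. If the rule also multiplies across 5 visits (0.05/55 = 0.0009), power is about 30%.

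**The case against.** The strongest reply is that the plan does contain a multiplicity procedure. With Tukey over all 12 means and a pooled error, the chance of any false marker difference across all 11 markers is already near 5%. It falls to between 1% and 5% if a significant group-by-visit term is also required. This stands. A reader might infer from the 43% that the error exceeds 5% however the plan is read; the documents do not support that. They do not establish the favourable reading either, because the Tukey family, error term and any gate are unstated. With the within-subject error the rate climbs to about 65%. Tukey also does nothing for markers sent to Mann-Whitney.

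A second reply is that only root coverage is powered, so the markers are exploratory in practice, and formal control of exploratory markers is partly a matter of taste. That is fair as to severity. But the SAP does not say so, and applies one level to every test alike.

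A third is that adjustment is costly and no choice of ANOVA term is best for every pattern of effect. At 0.0045 with 30 per arm, the group-by-visit term has only about 5% to 34% power for a lasting 0.5 SD difference (r from 0 to 0.7). The group term does better at low r (83% at r = 0) but has only 15% at r = 0.7. This is a reason to leave the choice of term to the sponsor, provided it is made in advance.

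**Conclusion.** The point holds. Eleven markers are tested at 0.05 each with nothing adjusting across them. With one test per marker, the chance of at least one false between-arm difference is 43% under independence and 13% to 38% for assumed r from 0.9 down to 0.3. With Mann-Whitney at each of 5 visits it is about 24% to 88% over the same range. In the ANOVA branch it can be anywhere from about 4% to about 65% on Tukey alone, depending on details the SAP omits.

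These figures rest on assumed correlations, two-sided tests and, in each scenario, all markers taking the same branch. They are scenarios, not bounds or estimates for this trial. A reader might also infer that the main result is compromised. It is not: root coverage at 6 months is a separate comparison, and its error rate does not depend on how the markers are tested.

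**What to change.** In the SAP:

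1. State that the between-group difference in root coverage at 6 months is the only confirmatory comparison, and that the markers are exploratory. Name the variable and test for it, since the SAP's list of analysed variables includes relative recession but not root coverage difference itself.
2. Fix one between-arm p-value per marker before unblinding. The choice of term is the sponsor's. The rule should cover both branches, including a marker that passes Shapiro-Wilk at some visits only.
3. Report Benjamini-Hochberg adjusted p-values at 5% across the 11 markers, beside unadjusted p-values and confidence intervals.
4. Describe a marker as differing between arms only if it passes the adjusted threshold, and call the rest hypothesis-generating.

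This changes wording only and needs no new data or patients. The downside is fewer marker claims and lower power for a single affected marker: about 84% down to 51% in the case worked above, or 30% if visits are also adjusted for. Lost samples reduce it further ("Strips contaminated with visible blood were discarded"): at 28 per arm the last figure is about 27%. Benjamini-Hochberg controls the false discovery rate. With 1, 3 or 5 strongly affected markers and the others independent, the chance of any false marker is about 9%, 14% and 15%.

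The document is written largely in the past tense. If the marker data have already been unblinded, the adjusted values can still be reported, but the choice of term should be labelled post hoc.
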